12.6.2 Deaths and Serious Adverse Events

A summary of serious TEAEs by SOC, PT, and maximum severity will also be presented by patient (not events). Patients can experience multiple events within the same SOC/PT, they will be counted only once in the most severe grade.

The following types of TEAEs will also be summarised by SOC and PT:

- Serious TEAEs
- Serious TEAEs Related to IMP
- TEAEs with a Fatal Outcome

Separate listings will be provided for all SAEs and all AEs with a fatal outcome.

12.6.3 Laboratory Data

Central laboratory data (haematology, serum chemistry, thyroid function) and local laboratory data (urinalysis) will be converted to Système International (SI) units. Any results containing the character values of "<" or ">" will be converted to the equivalent lower/upper limit of quantification (LLQ/ULQ). For each laboratory category and parameter noted in Table 4, absolute and change from baseline values will be summarised by analysis visit and treatment group using univariate statistics.

Shift tables of CTCAE grades from baseline to worst post-baseline will also be presented for the central laboratory data.

The change from baseline values for haematology, serum chemistry and thyroid function will be further summarised using box and whisker plots.

Standard reference ranges from the central laboratory will be used for the assessment of results being low, normal or high. Parameter results outside of the standard reference ranges will be flagged in the data listings.

Local laboratory urinalysis data will be listed only.

Table 4.	Laboratory	Parameters
----------	------------	------------

Category	Parameters			
Haematology	 Haematocrit Haemoglobin Absolute and Relative Reticulocyte Counts Red Blood Cell (RBC) Count White Blood Cell (WBC) Count Differential WBC Count 	 Platelet Count Absolute Neutrophil Count Mean Cell Volume International Normalised Ratio (INR) (Screening only). 		
Serum Chemistry	 Alkaline Phosphatase (ALP) Alanine Aminotransferase (ALT) Aspartate Aminotransferase (AST) Amylase Total and Conjugated Bilirubin Gamma-Glutamyltransferase (GGT) Glucose Total Protein 	 Albumin Creatinine Urea Total Cholesterol Triglycerides Sodium Potassium Chloride 		

Category	Parameters		
Thyroid Function	TSH and Free T4		
Urinalysis	pHProteinGlucoseKetones	 Bilirubin Blood Microscopic Examination of the Sediment 	
Pregnancy Test [†]	Serum Pregnancy TestUrine Pregnancy Test		

Note: Categories denoted with [†] will be listed only.

Note: WBC and Reticulocyte Counts will be expressed as absolute values. Differential counts will be expressed as both absolute counts and percentages of WBCs.

12.6.4 Vital Signs

Absolute and change from baseline values for pulse rate, SBP, DBP weight, oral temperature and body temperature will be summarised by analysis visit and treatment group using univariate statistics. The change from baseline for each parameter at each analysis visit will be further summarised using box and whisker plots by treatment group.

All vital signs data will be provided in a listing.

12.6.5 Physical Examinations, ECGs, and Other Observations Related to Safety

The absolute values and change from baseline values of each ECG parameter (Mean Heart Rate, PR Interval, QRS duration, QT interval, RR interval (see Section 10.11) and QTcF) will be summarised using univariate statistics at each analysis visit by treatment group. The interpretation of the ECG will be presented by result category (Abnormal Clinically Significant, Abnormal Non-Clinically Significant, Normal, Unevaluable and Unknown) at each analysis visit.

The absolute and change from baseline values for QTcF intervals will be further summarised using categorical intervals (see Section 10.11). Shift tables from baseline absolute interval to the maximum post baseline interval and maximum change from baseline interval will be presented.

All 12-lead ECG data will be provided in a listing, with abnormal interpretations flagged.

All physical examination findings will be provided in a listing only.

Baseline ECOG performance status will be summarised as part of the baseline characteristics, all ECOG data will be listed. The grading of ECOG performance status is defined in Section 10.12.

12.7 Pharmacokinetic Analyses

The PK Analysis Set will be used for PK analyses.

The initial PK analysis will be performed during the primary analysis, when all patients are expected to have had at least 3 cycles of pembrolizumab, at least one post-treatment scan, and the opportunity for a post-treatment tumour biopsy. The final pharmacokinetic analysis will be performed at the end of the study after DBL. If the predicted timing of the initial and final analyses are expected to be close in proximity, one analysis may be performed. The analysis will be reported formally and summarised for the CSR.

Observed plasma concentrations of setanaxib and GKT138184, along with blood sampling dates and actual blood sampling time relative to last dose, will be listed by patient, actual treatment (See Section 10.5.1), and nominal time point (Day 1, Week 3, Week 24, Week 51, Week 105, day of the second biopsy and at EoT). The listing would display the concentrations with the nominal time and actual time.

Observed plasma concentrations of setanaxib and GKT138184 will be summarised by actual treatment (See Section 10.5.1), nominal time point (Day 1, Week 3, Week 24, Week 51, Week 105, day of the second biopsy and at EoT) and

analyte (setanaxib or GKT138184) using univariate statistics (n, mean, geometric mean, median, standard deviation, standard error of the mean, coefficient of variation, minimum and maximum).

Further details regarding the PK analysis and exploratory PK/PD analyses will be provided in a separate PK analysis plan.

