5.4 Pharmacokinetics

Blood samples will be collected for measurement of plasma concentrations of setanaxib and its metabolite GKT138184 for all patients during the study at the visits specified in Table 1. The PK blood volumes to be collected during the study will be provided in the ICF and/or in the central laboratory manual.

PK samples will be collected just before the start of pembrolizumab infusion and before the IMP morning dose at Day 1, Week 3, Week 24, Week 51, and Week 105, and anytime for the PK samples taken on the day of the second biopsy and at EoT Visit.

Instructions for the collection and handling of biological samples will be provided by the sponsor (or designee) and will be included in the central laboratory manual. The actual date and time that each sample is collected will be recorded.

The measurement of plasma setanaxib and GKT138184 concentrations will be performed by a central laboratory.

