6 TREATMENTS

6.1 Investigational Medicinal Product

6.1.1 Description of Investigational Medicinal Product

Test Product	
IMP/non-IMP:	IMP
Name:	Setanaxib
Dose:	800 mg BID (2 tablets in the morning and 2 tablets in the evening) Setanaxib tablets will contain 400 mg setanaxib powder formulated with excipients.
Mode of administration:	Orally (or via either a feeding tube or a percutaneous endoscopic gastrostomy device in case patients are unable to swallow tablets)
Manufacturer:	Aptuit [name]
Placebo	
Substance:	Matching placebo tablets, containing only excipients, will be provided. The placebo tablets will be visually identical to setanaxib tablets to maintain the blind.
Dose:	Not applicable
Mode of administration:	Orally (or via either a feeding tube or a percutaneous endoscopic gastrostomy device in case patients are unable to swallow tablets)
Manufacturer:	Aptuit [name]

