6.4.1 Dose Modification

Dose interruptions are required in case of anaemia and hypothyroidism, when the events meet the criteria as defined in Section 5.3.2.1, and Section 5.3.2.2, respectively. Events that require permanent discontinuation of IMP are listed in Section 4.3.1.

Dose reduction of setanaxib to 400 mg BID to manage anaemia, hypothyroidism, or any Grade 3 or otherwise intolerable toxicity, which is considered related to setanaxib may be instituted at the investigator's discretion after discussion with the medical monitor.

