8.4.7 Pharmacokinetic Endpoints

The PK Analysis Set will be used for PK analyses.

Plasma concentrations of setanaxib and GKT138184, along with blood sampling dates and actual blood sampling time relative to dosing time, will be listed by dose group, patient, and nominal sampling time. Pre-dose and post-dose plasma concentrations of setanaxib and GKT138184 will be summarised as appropriate. AUC(0-24)-ss, Cmin-ss and Cmax-ss will be estimated for each individual patient using non-linear mixed effect methodology and prior PK knowledge of the compound, and summarised as appropriate. More details regarding the PK analysis and exploratory PK/PD analyses will be provided in a separate pharmacokinetic analysis plan.

An interim pharmacokinetic analysis will be performed at the initial data cut-off approximately 9 weeks after completion of enrolment, when all patients are expected to have had at least 3 cycles of pembrolizumab, at least one post-treatment scan, and the opportunity for a post-treatment tumour biopsy. This analysis will result in an interim report.

The final pharmacokinetic analysis will be performed at the end of the study after database lock. If the predicted timing of the initial and final analyses are expected to be close in proximity, only one analysis may be performed. Only the final analysis will be reported formally and summarised for the CSR.

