10.5 Study Drug Exposure

10.5.1 Actual Treatment Assignment

The actual treatment assigned to a patient will be the treatment that the patient first received regardless of any dispensing issues at a later visit. For example, if a patient was randomised to the placebo+pembrolizumab group but the patient's first dose in the study was setanaxib+pembrolizumab, they will be assigned as having an actual treatment as the setanaxib+pembrolizumab group they first received, even if they were later dispensed placebo+pembrolizumab at all remaining visits.

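### SAP 12.7 summarises drug concentrations without regard to the dose being taken at sampling, so reduced-dose, interrupted and any-time samples can blur a descriptive PK row

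*SAP*

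**What the plan says.** SAP 12.7 sets the layout of the concentration table: "Observed plasma concentrations of setanaxib and GKT138184 will be summarised by actual treatment (See Section 10.5.1), nominal time point" and analyte. The statistics include the mean, geometric mean, median, coefficient of variation, minimum and maximum. The companion listing shows actual sampling time relative to last dose. Further PK detail is left to a separate plan.

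SAP 10.5.1 defines the grouping variable. Actual treatment "will be the treatment that the patient first received regardless of any dispensing issues at a later visit". Its worked example keeps a patient in the setanaxib group even when placebo was dispensed at every later visit.

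Protocol 6.4.1 allows the dose to change during the study: "Dose reduction of setanaxib to 400 mg BID to manage anaemia, hypothyroidism, or any Grade 3 or otherwise intolerable toxicity" is permitted at the investigator's discretion. The same section adds: "Dose interruptions are required in case of anaemia and hypothyroidism", when set criteria are met.

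Protocol 5.4 takes the Day 1, Week 3, 24, 51 and 105 samples before the morning dose, but allows "anytime for the PK samples taken on the day of the second biopsy and at EoT Visit".

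Protocol 8.4.7 says concentrations "will be listed by dose group, patient, and nominal sampling time". For summaries it leaves the format open. It obtains AUC(0-24)-ss, Cmin-ss and Cmax-ss for each patient from a mixed-effects model.

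**The concern.** A concentration is interpretable only alongside the dose being taken and the time since it was taken. The 12.7 table has neither. The first-treatment rule is a reasonable convention for safety tables, where a patient needs one label for the whole study. In a concentration table, each sample needs its own label.

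At stake is how a reader interprets the one PK summary whose layout the SAP sets out. Plasma exposure is a secondary objective. Protocol 3.2, Table 3 gives a metabolite AUC margin of 0.7 at Week 39, calculated with human data from Day 8. Understating later concentrations at 800 mg BID would therefore err in the less cautious direction. No document says that this table will be used to revisit that margin.

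**Working it through.** The documents give no figure for this table to reproduce. The check has two parts: following the rules as written, and illustrating the size of the effect.

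**Following the rules**

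- *Reduced dose or interruption.* Table rows are defined by treatment, visit and analyte. A setanaxib patient on 400 mg BID, or off drug at Week 24, falls in the same row as a patient on 800 mg BID. The cause is the missing dose level, not SAP 10.5.1.
- *Misdispensing.* Here SAP 10.5.1 is the cause. A sample taken on placebo stays in the setanaxib row if setanaxib was received first. In the reverse case, drug concentrations appear under placebo.
- *Biopsy day and EoT.* SAP 12.7 gives each its own row, but within a row the time since last dose varies. EoT follows permanent discontinuation (Protocol 3.1), so time off drug varies too.
- *Windowing.* SAP 10.4 assigns EoT visits to analysis visits whatever their eCRF label, and prefers the scheduled sample when both fall in one window. With no scheduled sample, an any-time EoT sample could become the Week 24 or Week 51 value. SAP 12.7 keeps EoT as a separate time point. The two sections do not agree.

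**Size, for illustration**

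Inputs: Protocol 3.2 expects 12 of 25 setanaxib patients to be treated for at least 6 months and 8 for at least 12 months. These stand in for n at Weeks 24 and 51. Assumptions: troughs proportional to dose, patients otherwise alike, k of n patients affected. The documents give no value for k.

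Formulas, as a ratio to a row containing only 800 mg BID samples:

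- k at half dose: arithmetic mean 1 − k/(2n); geometric mean 0.5^(k/n).
- k near zero: arithmetic mean 1 − k/n.

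| | n=12 (Week 24) | n=8 (Week 51) |
|---|---|---|
| 0 affected | 1.00 | 1.00 |
| 1 at 400 mg BID, arithmetic | 1 − 1/24 = 0.958 | 1 − 1/16 = 0.938 |
| 1 at 400 mg BID, geometric | 0.5^(1/12) = 0.944 | 0.5^(1/8) = 0.917 |
| 3 at 400 mg BID, arithmetic | 1 − 3/24 = 0.875 | 1 − 3/16 = 0.812 |
| 3 at 400 mg BID, geometric | 0.5^(3/12) = 0.841 | 0.5^(3/8) = 0.771 |
| 1 near zero, arithmetic | 1 − 1/12 = 0.917 | 1 − 1/8 = 0.875 |

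The geometric mean is more sensitive to a very low value. If one interrupted sample is 10% to 1% of typical, the ratio is 0.1^(1/12) to 0.01^(1/12), a fall of 17% to 32% at n=12. At n=8 the fall is 25% to 44%. SAP 9.2.6 counts a value below the quantification limit as measured, but 12.7 does not say what number it takes.

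If enrolment reaches 70, with 35 per arm and the same proportions, n is about 35 × 12/25 = 17 and 35 × 8/25 = 11. One patient at half dose then lowers the arithmetic mean by 1/34 = 2.9% or 1/22 = 4.5%.

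**The case against.** The strongest reply is that the exposure endpoints do not come from this table. AUC(0-24)-ss, Cmin-ss and Cmax-ss are estimated per patient from a model, which can use individual doses and sampling times, and the PK plan is not among the documents. This stands. A reader might infer that the trial's reported exposure will not be that of the study dose; the documents do not support that.

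A reader might also infer that any-time samples are averaged with troughs. Under 12.7 they are not, because biopsy day and EoT have their own rows. Only the windowing rule in SAP 10.4 leaves a route for EoT samples to enter a scheduled visit. The mixed times within those two rows follow from the protocol's sampling scheme, and no document offers either row as a trough estimate.

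It is tempting to say that the SAP silently dropped the protocol's dose grouping. Protocol 8.4.7 applies that term to the listing only. With one randomised active dose it may simply mean study arm. The SAP also cites protocol v5.0, whereas the version supplied is v4.0. An undeclared change cannot be established.

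Finally, reductions are discretionary and interruptions trigger a retest within 7 days (anaemia) or 5 days (hypothyroidism), so few may coincide with a PK visit. Splitting 8 to 12 patients further could leave cells of one or two. Both points are fair and limit the size of the problem. They do not supply the missing rule. The SAP itself plans to tabulate dose reductions and missed doses (12.3.1), so it expects some.

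**Conclusion.** The point holds for a descriptive secondary table. Followed as written, SAP 12.7 places samples on 800 mg BID, on 400 mg BID, during interruption and after misdispensing in one row, and gives a single mean for samples drawn at different times since last dose. If affected samples occur, the row understates concentrations at 800 mg BID. The arithmetic mean falls by about 4% (n=12) or 6% (n=8) for one patient on 400 mg BID, and by about 8% or 12.5% for one near-zero sample.

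These figures rest on dose-proportional troughs and on the protocol's expected numbers still on treatment. The real frequency is not given, so a flat statement that the table is biased low from Week 24 onward is not supported; with no affected samples the effect is zero. Neither the model-based PK parameters nor the primary analysis is shown to be affected.

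**What to change.** In SAP 12.7:

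- Classify each sample by the drug and dose being taken at sampling, not by the treatment first received.
- Summarise samples on 800 mg BID, and show reduced-dose and interrupted or off-drug samples separately. If there are few, list or flag them.
- Present biopsy-day and EoT concentrations against actual time since last dose instead of as one mean.
- Reconcile the EoT windowing in SAP 10.4 with the separate EoT time point in 12.7.

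If the PK analysis plan already does this, a cross-reference from 12.7 is enough.

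The cost is SAP wording and minor programming. Dose times before PK visits (Protocol 6.4) and interruption dates (Protocol 6.10) are already collected. The downside is smaller cells, which is why listing or flagging is preferable when few samples are affected.

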14.0 Glossary of Abbreviations

Glossary of Abbreviations:		
ADI	Actual Dose Intensity	
AE	Adverse Event	
AESI	Adverse Event of Special Interest	

Glossary of Abbreviations:			
ALP	Alkaline Phosphatase		
ALT	Alanine Aminotransferase		
ANCOVA	Analysis of Covariance		
AST	Aspartate Aminotransferase		
ATC	Anatomical Therapeutic Chemical		
BLQ	Below the Quantification Limit		
BOR	Best Objective Response		
CAF	Cancer-Associated Fibroblast		
CD8⁺	Cluster of Differentiation 8		
CI	Confidence Interval		
CR	Complete Response		
eCRF	Electronic Case Report Form		
CTCAE	Common Terminology Criteria for Adverse Events		
DBP	Diastolic Blood Pressure		
DCR	Disease Control Rate		
DoR	Duration of Response		
dp	Decimal Point		
ECG	Electrocardiogram		
ECOG	Eastern Cooperative Oncology Group		
EoT	End of Treatment		
FAS	Full Analysis Set		
GGT	Gamma-Glutamyltransferase		
HPV	Human Papillomavirus		
ICH	International Council for Harmonisation		
IDMC	Independent Data Monitoring Committee		
IMP	Investigational Medicinal Product, referring to Setanaxib/Placebo		
INR	International Normalised Ratio		
IRT	Interactive Response Technology		
IV	Intravenous		
LFC	Limit Fold Change		
LLQ	Lower Limit of Quantification		
LS	Least Squares		
MedDRA	Medical Dictionary for Regulatory Activities		
NCI	National Cancer Institute		
NTL	Non-Target Lesion		
ORR	Overall Response Rate		
OS	Overall Survival		
PD	Progression of Disease		
PD-L1	Programmed Cell Death Ligand 1		

Glossary of Abbreviations:			
PFS	Progression-Free Survival		
PHP	Hypertext Preprocessor		
PK	Pharmacokinetics		
PPS	Per Protocol Analysis Set		
PR	Partial Response		
PSO	ICON System of Record		
PT	Preferred Term		
RBC	Red Blood Cell		
RDI	Relative Dose Intensity		
RECIST	Response Evaluation Criteria in Solid Tumours		
RNA	Ribonucleic Acid		
SAP	Statistical Analysis Plan		
SAE	Serious Adverse Event		
SBP	Systolic Blood Pressure		
SCCHN	Squamous Cell Carcinoma of the Head and Neck		
SD	Stable Disease		
SI	Système International		
SMA	Smooth Muscle Actin		
SOC	System Organ Class		
TEAE	Treatment-Emergent Adverse Event		
TIL	Tumour-Infiltrating Lymphocytes		
TL	Target Lesion		
TNM	Tumour, Node, Metastasis		
ULQ	Upper Limit of Quantification		
WBC	White Blood Cells		
WHO	World Health Organization		
WHODD	World Health Organization Drug Dictionary		

15.0 Appendix

15.1 Handling of Partial Adverse Event and Medication Dates

If the imputation rules specified here result in illogical dates, adjust accordingly. If any estimated start date is after a complete/imputed end date, set the start date to be the first day in the end date month. If any estimated end date is prior to a complete/imputed start date set to be the last day of the start date month.

Date of Interest	Missing	Condition	Imputation
AE start date	Day	M and Y is the same as M and Y of first dose of IMP	Date of first dose of IMP

Table 5. Handling of Partial AE Dates

Date of Interest	Missing	Condition	Imputation
		Y is prior to Y of first dose of IMP	Last day of the month
		Y is the same as Y of first dose of IMP, M is prior to M of first dose of IMP	Last day of the month
		M and/or Y is after first dose of IMP	First day of the month
	Day, Month	Y is the same as the Y of first dose of IMP	Date of first dose of IMP
		Y is prior to Y of first dose of IMP	Use 31 st of December
		Y is after Y of first dose of IMP	Use 1 st of January
	Month	Treat day as missing and use imputation rules for D and M as missing	See Day, Month imputation rules
	Day, Month, Year	None-date is completely missing	Date of first dose of IMP
AE End Date	Day	M and Y same as date of last dose of IMP	Date of last dose of IMP
		M and Y not the same as date of last dose of IMP/date of last dose of IMP is missing	Set to the last day of the month, or the end of study/death date whichever is earliest
	Day, Month	Y is the same as last dose of IMP	Date of last dose of IMP
		Y is not the same as date of last dose of IMP/date of last dose of IMP is missing	Set to 31 st of Dec, or the end of study/death date whichever is earliest
	Day, Month	Treat day as missing and use imputation rules for D and M as missing	See D, M imputation rules
	Day, Month, Year	None	No imputation, assume Ongoing

Note: D=Day, M=Month, Y=Year.

Table 6. Handling of Partial Medication Dates

Date of Interest	Missing	Condition	Imputation
Medication start date	Day	M and Y is the same as M and Y of first dose of IMP	Date of first dose of IMP
		M and/or Y is not the same as the first dose of IMP	First day of the month
	Day, Month	Y is the same as the Y of first dose of IMP	Date of first dose of IMP
		Y is not the same as first dose of IMP	Use 1 st of January
	Month	Treat day as missing and use imputation rules for D and M as missing	See D, M imputation rules
	Day, Month, Year	None-date is completely missing	Assume prior and concomitant. Impute as the last day prior to the first dose of IMP.
Medication End Date	Day	M and Y same as date of last dose of IMP	Date of last dose of IMP
		M and Y not the same as date of last dose of IMP/date of last dose of IMP is missing	Set to the last day of the month, or the end of study/death date whichever is earliest
	Day, Month	Y is the same as last dose of IMP	Date of last dose of IMP

Date of Interest	Missing	Condition	Imputation
		Y is not the same as date of last dose of IMP/date of last dose of IMP is missing	Set to the 31 st of Dec, or the end of study/death date whichever is earliest
	Month	Treat day as missing and use imputation rules for D and M as missing	See D, M imputation rules
	Day, Month, Year	None	No imputation, assume Ongoing

Note: D=Day, M=Month, Y=Year.

